1.3 SCHEDULE OF ACTIVITIES

All participants will self-refer to an initial appointment (i.e., intake) at their CCC, and as part of standard operating procedures will meet with an intake counselor, either in-person or remotely following practices of the CCC, as a first step to access CCC services. As part of the CCC's standard clinic workflow, all students seeking services will complete the Counseling Center Assessment of Psychological Symptoms (CCAPS-62). Students who meet inclusion and exclusion criteria will be given a brief explanation of the study by the intake counselor. Interested students will be scheduled for an appointment conducted either in-person or remotely with a member of the research who will review the consent form with each student. Students who sign the consent form will then complete a baseline assessment with the Independent Evaluator (IE), either online or in-person.

The schedule of activities for the CAMPUS Trial is presented in Table 1 on the next page.

Table 1. Schedule of Activities for the CAMPUS Trial

	-1	0	Stage 1						Stage 2						26
			1	2	3	4	5	6	7	8	9	10	11	12	13
Completed by CCC Intake Counselor															
Screening Data Form*		X													
Completed by Student Participants															
Demographic Information			X												
Sexual Orientation and Gender Identity		X													
Counseling Center Assessment of Psychological Symptoms (CCAPS)	X	X	X	X	X	X	X	X	X	X	X	X	X	X	X
Clinical Global Impression – Severity (CGI-S)		X			X			X			X				X
Clinical Global Impression – Improvement (CGI-I)					X			X			X				X
Adverse Events and Serious Adverse Events (AE/SAE)		X	X	X	X	X	X	X	X	X	X	X	X	X	X
Difficulties in Emotional Regulation Scale (DERS)		X						X			X				X
DBT Ways of Coping Checklist (WCCL)		X						X			X				X
Acceptance and Action Questionnaire (AAQ)		X						X			X				X
Suicide Cognitions Scale (SCS)		X			X			X			X				X
Self-Efficacy for Managing Emotions		X			X			X			X				X
Optimism Hope Scale (OHS)		X			X			X			X				X
Personality Assessment Inventory-Borderline Features Scale (PAI-BOR)		X													
Life Stressor Checklist-Revised (LSC-R)		X													X
Drug Abuse Screening Test (DAST)		X													X
Alcohol Use Disorders Identification Test (AUDIT)		X													X
Student Treatment Credibility Questionnaire (STCQ)				X					X						
Student Treatment Expectations Questionnaire (STEQ)			X						X						
Client Satisfaction Questionnaire (CSQ)								X							X
Academic Functioning		X													X

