While the identification of transdiagnostic mechanisms of change has become a high priority in suicide research, there is a paucity of research on mechanisms of change within suicide-focused treatments.⁷⁹ Bryan⁸⁰ has hypothesized that evidence-based treatments for suicidal risk (SR) share three common mechanisms of change: cognitive flexibility, emotion regulation, and cognitive reappraisal. This aligns with the CAMS and DBT literature.^{7,81} CAMS purports to create therapeutic change through an intentional collaborative approach to treatment: assessment of SR; suicide-specific treatment planning; deconstruction of, and problem-solving for, patient-defined suicidal “drivers;” and an explicit focus on reasons for living.⁷ Thus, CAMS is entirely suicide-focused and known/predicted mediators of change include reductions in suicidal cognitions⁸² and suicide-focused attentional bias.^{82,83} The putative mechanisms unique to DBT are quite different: hierarchical targeting of problems, mindfulness, dialectical focus, emotion regulation, distress tolerance, counselor self-disclosure, chain analysis, commitment strategies, validation, and telephone consultation.⁸¹ Among these, the research-supported mediators for DBT include skills use,⁸⁴ self-efficacy for managing emotions,¹⁸⁸ and emotion regulation/experiential avoidance.⁸⁴⁻⁸⁶

The CAMPUS Trial is adequately powered (moderate effect size estimates) to examine known and putative mechanisms of change in CAMS and CC-DBT and whether each works through different or overlapping mechanisms. In addition to known mediators, we will investigate promising exploratory ones identified through RDoC⁷⁹ and SR-based⁸⁷ reviews.

The Proposed Methodology Is Innovative for Suicidal Risk (SR) Interventions

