9.2 CAMPUS TRIAL SAMPLE SIZE DETERMINATION

Power for Aim 1:

Sample size for the study is based primarily on Aim 1, although we also provide effect size (ES) estimates for the other aims given the proposed sample size. With respect to Aim 1, with a total sample of 480, the approach provided by Crivello and colleagues^{178,179,180} guarantees that the adaptive intervention with the lowest estimated mean suicide risk (ideation + behaviors) at post-treatment is, in fact, the best adaptive intervention with 90% probability. This calculation assumes that the best two ATSSs differ by $d = 0.25$ (or ≥ 2 points on the SSI), which corresponds to a small ES estimate.¹⁸¹

Power for Aim 2:

Aim 2 is a two-sample comparison (cells A+B+C vs. D+E+F). Using a two-side, two-sample t-test based on Type-I error rate of 2.5%, a sample of 240 randomized to each Stage 1 treatment arm (N=480 total), we will have 85% power to detect a small, standardized ES of $d = 0.30$ in the between groups difference in change on the primary outcomes. Based on prior studies and our pilot data with $SD=7$ for SSI,¹¹³ this ES corresponds to a clinically meaningful difference of 2 in the SSI. Note that this is a conservative estimate of power: in the repeated measures LMM, power increases in proportion to the within person correlation in baseline to 26-week SSI which can be as high as 0.40 ($p < .01$, based on pilot data). At 3-month follow-up (assuming a baseline to 48-week within correlation of 0.3) we will have 94% power to detect the same moderate ES.

Power for Aim 3:

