Assuming about 50% response (N=240) and about 50% insufficient response rate [N=240, which is chosen to be slightly higher for a value divisible by the four possible treatment paths from Stage 1 to Stage 2 (CAMS-CAMS, CAMS-DBT, TAU-CAMS, and TAU-DBT) (based on pilot data)] to Stage 1 treatments corresponding to N=60 potential student participants to be randomized to each of the 4 Stage 2 arms among the non-responders as illustrated in the Schema Figure in section 1.2. We anticipate an at most Stage 1 attrition rate of about 25% among those with an insufficient response leaving N=180 total student participants to be randomized in Stage 2 (approximately 45 student participants per ATS). Estimates of attrition are chosen as equal across each treatment path but are in essence worst case scenarios, where we may see less attrition for specific treatment paths compared to others; therefore, all power estimates are conservative, with more power achievable with more available student participants for different treatment combinations. Based on the method outlined by Oetting and colleagues¹⁸² and a within-person correlation of 0.60, 2.5% Type-I error, we will have over 80% power to detect a difference of ≥ 3.4 ($d = 0.34$) in change in SSI between DBT vs. CAMS.

Power for Aims 4 and 5:

Best practices for power calculations for mediation and moderation models within SMART designs are still debated. For mediation, we will use the work of Fritz and MacKinnon,¹⁸³ who document sample size requirements to guarantee 80% power under the sequential regression framework¹⁶⁶ and the formulas of Vittinghoff et al.¹⁸⁴ Under the assumption of a medium effect for intervention on the mediator and a medium effect for intervention on outcome covarying

the mediator, and an alpha=0.025, the total sample size is calculated as N=166. Therefore, our design consisting of a sample size of 480 within Stage 1 and at least 90 subjects per two Stage 2 arms (CAMS vs CC-DBT) (N=180 total), is sufficiently powered to detect mediation within Stage 2. For moderation, we use Cohen's¹⁸¹ power tables, our sample size of 480 at the start of Stage 1 and at least 90 subjects per arm at Stage 2 is more than sufficient to detect a medium-to-large ES for a moderator.

Table 8. The 4 Adaptive treatment strategies embedded in the proposed SMART					
Adaptive Treatment Strategy	Stage 1 Treatment	Status at End of Stage 1	Stage 2 Treatment	Cells Involved in Comparisons	

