9.3.3 ANALYSIS OF THE SECONDARY ENDPOINT(S)

AIMS 1-3 analyses are the same as the preceding subsection 9.4.2.

AIM 4 analyses focus on treatment-specific mediation in both CAMS and CC-DBT. The potential mediators (for CC-DBT: DERS, DBT-WCCL, and AAQ; for CAMS: SCS, OHS; Self-Efficacy,) are assessed at baseline, midpoints, and endpoints. To maintain the temporal sequence order of the mediator per Kraemer and colleagues,¹⁶⁵ mediation occurs when, after partialling out the change in the mediator (baseline through midpoints), the relationship between intervention condition and the change in outcome from midpoint(s) through endpoint, when controlling for early change in the outcome (baseline to midpoint), is significantly reduced (in full mediation the relationship is zero). Standard mediation analyses¹⁶⁶ assume sequential ignorability. We will implement causal mediation approaches,^{167,168} as described by MacKinnon and colleagues,¹⁶⁹ which provide an adjustment due to potential unmeasured confounding and the violation of the assumption of sequential ignorability. The analysis team has experience implementing these models.^{170,171} VanderWeele's research team¹⁷² recently described the above mediation technique specifically suited for LMM framed under a generalized mixed effects structure, which we will incorporate. We will fit separate causal mediation models for Stage 1 and Stage 2. Exploratory analyses will focus on multiple mediation and moderated mediation within the causal mediation framework.

AIM 5 analyses focus on moderation within Stage 1 and Stage 2 (gender identity, sexual orientation, minority culture, number of prior suicide attempts, AUDIT, DAST, PAI-BOR, OHS, GAS). A moderator is a baseline characteristic that has a differential effect on outcome across intervention condition¹⁶⁵ and, in the context of a SMART, could be used to further individualize treatment to a particular student participant. Note that a predictor is a non-specific

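### The Background claims adequate power to tell whether CAMS and CC-DBT work through different or overlapping mechanisms, but the only mediation sample size covers a single mediator, and no test of overlap is planned.

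*Combined protocol and SAP*

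**What the plan says.** Section 2.2 (Background, on mechanisms of change) calls the trial "adequately powered (moderate effect size estimates) to examine known and putative mechanisms of change in CAMS and CC-DBT and whether each works through different", with overlap named as the alternative. The power claim therefore reaches past single mediators to a comparison of the two treatments.

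Table 2 in Section 3 sets two treatment-specific hypotheses. Under 4a, suicide-focused processes mediate CAMS versus TAU. Under 4b, emotion regulation, self-efficacy and skills mediate DBT versus Stage 2 CAMS.

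Section 9.3.3 assigns mediators by treatment and gives their timing: "The potential mediators (for CC-DBT: DERS, DBT-WCCL, and AAQ; for CAMS: SCS, OHS; Self-Efficacy,) are assessed at baseline, midpoints, and endpoints". It fits separate models for each stage and leaves multiple and moderated mediation to exploratory work.

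Section 9.2 relies on published work said to "document sample size requirements to guarantee 80% power" and, for two medium effects, states: "alpha=0.025, the total sample size is calculated as N=166". It compares that figure with 480 students in Stage 1 and 180 in Stage 2, and concludes that mediation can be detected within Stage 2.

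**The concern.** Detecting one mediator in one comparison is a different question from asking whether two treatments share a mechanism. The second question needs the same mediator examined for both treatments, with either a contrast of indirect effects (for difference) or a margin (for overlap). Sections 3, 9.2 and 9.3.3 contain no such contrast, margin, decision rule or power.

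The two planned comparisons also differ in population (all randomized students versus Stage 1 non-responders) and in comparator (TAU versus CAMS). Setting a significant result in one beside a non-significant result in the other would therefore not establish distinct mechanisms. What is at stake is a published statement about mechanisms that cites a power claim which does not apply to it.

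**Working it through.** **Inputs.** From Section 9.2: alpha 0.025, 80% power, N=166, Stage 1 N=480, and Stage 2 N=180 (240 non-responders less 25%). The sidedness of the mediation test is not stated. I take it as two-sided, as for Aim 2 ("Using a two-side, two-sample t-test based on Type-I error rate of 2.5" percent), so z = 2.241.

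The plan gives no numbers for medium. I assume a treatment effect on the mediator of a = 0.5 SD and a mediator-outcome partial r of 0.30, so b = 0.30/√(1 − 0.09) = 0.3145. Section 9.2 words its second medium effect as the intervention's effect on outcome given the mediator, which is the direct effect. The mediator-to-outcome path is therefore my assumption.

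**Step 1: reproduce N=166.** Joint-significance power for one mediator is Φ(a√(N/4) − z) × Φ(b√N − z).
- N=164: Φ(3.202 − 2.241) × Φ(4.028 − 2.241) ≈ 0.83 × 0.96 ≈ 0.80.
- A regression formula with a direct effect of d = 0.5 (0.25 per SD of treatment) and treatment-mediator correlation 0.30 gives (2.241 + 0.842)²/0.25²/(1 − 0.09) = 167.1.

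Both bracket 166, and both are single-mediator calculations. With b = 0.39 the joint test needs 154. With both standardized paths at 0.39 it needs only 81.

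**Step 2: the claim that Section 9.2 supports.** At N=180, Φ(3.354 − 2.241) × Φ(4.219 − 2.241) = 0.867 × 0.976 = 0.85; simulation gives about 84%. At N=480 the power exceeds 0.99.

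**Step 3: the claim in Section 2.2.** Compare one mediator's indirect effect ab across the two comparisons, using the delta-method variance a²/N + 4b²/N. The estimates are treated as independent. This is an approximation, because Stage 2 students are a subset of Stage 1. Here ab = 0.157.
- Present in Stage 1, absent in Stage 2: variance 0.001345 + 0.002198 = 0.003543, SE 0.0595. Power Φ(0.157/0.0595 − 2.241) = Φ(0.40) = 0.66.
- Present in Stage 2, absent in Stage 1: variance 0.003587 + 0.000824 = 0.004411, SE 0.0664. Power Φ(0.13) = 0.55.
- Full in Stage 1, half in Stage 2 (a halved): variance 0.001345 + 0.002545 = 0.003890, SE 0.0624, difference 0.0786. Power Φ(−0.98) = 0.16. The reverse direction gives 0.14, and a simulation gave about 13%.
- Equivalence within half the effect: SE = √(0.001345 + 0.003587) = 0.0702. Even at a one-sided 5% level the interval half-width is 1.645 × 0.0702 = 0.115, wider than the margin of 0.079. Equivalence could not be concluded.

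**Step 4: sensitivity.**

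| Assumption | Stage 1/Stage 2 N | Present vs absent | Half vs full | N implied for one mediator |
|---|---|---|---|---|
| a = 0.5 SD, b = 0.3145 | 480/180 | 0.55-0.66 | 0.16 | 164 |
| a = 0.5 SD, b = 0.39 | 480/180 | 0.61-0.68 | 0.18 | 154 |
| both standardized paths 0.39 | 480/180 | 0.88-0.96 | 0.35 | 81 |
| a = 0.5 SD, b = 0.3145, illustrative 25% further loss | 360/135 | 0.42-0.52 | 0.13 | 164 |

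**Step 5: discordant significance.** If a mediator worked equally in both comparisons at 480/180, the two tests would still disagree in about 0.999 × (1 − 0.846) + 0.001 × 0.846 ≈ 15% of trials.

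**Step 6: schedule and lists.** In Table 1 the row for "Difficulties in Emotional Regulation Scale (DERS") and the rows for WCCL and AAQ each carry four marks. SCS, OHS and Self-Efficacy carry five. Lined up row by row, the missing mark is mid-Stage 1. The table layout is broken in the text, so this is an apparent gap. If real, it conflicts with Section 9.3.3, and the baseline-to-midpoint change could not be formed for those three measures in Stage 1. Self-efficacy is a DBT mediator in Section 2.2 and hypothesis 4b, but follows the CAMS list in Section 9.3.3.

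**The case against.** The strongest reply is that hypothesis 4b is head to head. A significant indirect effect through a DBT mediator in CC-DBT versus CAMS is a real test that CC-DBT works through it more than CAMS does. That stands. A reader might infer that no difference in mechanism is tested anywhere, and the documents do not support that.

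A reader might also infer that the plan intends to declare mechanisms different whenever one mediator is significant and another is not. No section states such a rule; the 15% above describes a risk of interpretation only.

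A third tempting step is to contrast two mediators' indirect effects within CC-DBT versus CAMS (a1b1 − a2b2) and quote its power, roughly 20-40% under some assumptions, as the power for overlap. That contrast compares two mediators for one treatment comparison. A mechanism that both treatments share equally gives an indirect effect near zero there, so the contrast cannot show overlap.

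It is also fair that Section 2.2 is rationale, that Section 9.2 limits its own conclusion to detecting mediation within Stage 2, that Aim 4 is secondary, and that the Table 1 gap blocks neither stated hypothesis: 4b needs the DBT mediators only in Stage 2. These replies limit the weight of the point. They do not supply the missing test or power.

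**Conclusion.** The point holds as an overstated power claim. Section 9.2 supports detecting one mediator in Stage 2, at about 84% power. It does not support adequate power for the different-or-overlapping question.

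Three parts of that question have neither a test nor a power figure: the CAMS mediators under CC-DBT, the DBT mediators under CAMS versus TAU, and overlap itself. Power across the two comparisons is about 55-68% for present versus absent and about 13-18% for half versus full, with essentially none for equivalence.

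These figures rest on assumed medium values (a = 0.5 SD, partial r about 0.30, with b = 0.39 at the upper end), two-sided alpha 0.025, N=480 and N=180, and no loss during follow-up. Present-versus-absent power reaches 88-96% only if both standardized paths are 0.39, and that reading does not fit N=166. The primary aim is unaffected.

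**What to change.** - **Section 2.2:** limit the adequate-power statement to detecting single mediators, and label the question of different or overlapping mechanisms exploratory.
- **Section 9.3.3, models:** also test SCS and OHS in the Stage 2 CC-DBT versus CAMS model, and report every indirect effect with its interval.
- **Section 9.3.3, interpretation:** state that different mechanisms will not be inferred from one mediator being significant and another not, and that overlap will not be inferred from a non-significant or equal indirect effect. Do not print a power for a1b1 − a2b2 as the power for overlap.
- **Section 9.3.3 and Table 1:** reconcile the timing of DERS, DBT-WCCL and AAQ. If there is no mid-Stage 1 assessment, say that these mediators are not tested in Stage 1.
- **Self-efficacy:** assign it consistently across Sections 2.2, 3 and 9.3.3.

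The cost is wording plus a few extra models on measures already scheduled. No new data collection is needed. The one downside is a slightly less favourable power statement for a secondary aim.

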2.3 RISK/BENEFIT ASSESSMENT

2.3.1 KNOWN POTENTIAL RISKS

Risk 1. Worsening of symptoms because of the interventions. With any intervention, there is always the risk that the intervention will affect the individual negatively. There is a slight risk that discussing suicidality specifically or feeling dejected by lack of improvement may increase psychological distress, including suicidal thoughts and behaviors, during and possibly following the completion of the intervention. As there is not an extensive literature on the impact of suicide-focused care via teletherapy, it is unknown whether the remote arrangement of teletherapy in the CAMPUS trial will lead to a greater risk of worsening symptoms because of interventions.

Risk 2. Breach of confidentiality. There is a slight risk that participants will have their privacy violated if information about them is not kept confidential or if participants’ online data is accessed by unauthorized users. Participants’ discussions of imminent suicidality/homicidality, child abuse/neglect, or elder abuse/neglect may result in a breach of confidentiality (including within the campus) due to counselors’ duty to report. In addition, as some clinical care and assessments will be provided through online platforms, there is a risk that private clinical communications could be “hacked” by third parties which might compromise confidentiality. Further, if participants are not alone in private spaces during assessments or therapy sessions, other people may hear personal information about the participant.

Risk 3. Emotional distress associated with assessments. There is a slight risk that assessments with questions about sensitive topics like suicidal ideation and behaviors, substance abuse, gender identity, and sexual orientation may result in increased distress and potentially increased suicidality.

Risk 4. Being involuntarily hospitalized. There is a slight risk that participants in this study, given that they are moderately to severely suicidal, may be civilly committed to a psychiatric setting involuntarily.

Risk 5. Feeling coerced to participate in the study. Because participation in the study will start within a clinical setting (the CCCs), there is a slight possibility that participants will feel pressured to be part of the study.

2.3.2 KNOWN POTENTIAL BENEFITS

There are several potential direct (and indirect) benefits of the CAMPUS trial to the participants and to the greater public. In the wake of the COVID-19 pandemic, there is little empirical knowledge about the effectiveness of online training for clinicians and delivery of suicide-focused care via teletherapy. As pandemically-driven public health requirements include physical distancing and the use of masks, and generally reduce interpersonal contact, there are many compelling arguments for carefully studying the effectiveness of online training and delivery of care.

A hybrid teletherapy/in-person model of treatment delivery would also provide CCCs with the flexibility to move treatment online seamlessly in the event of campus shutdowns in the future or even as part of regular campus operations, given that residential students leave their campuses during academic breaks. As noted previously, considering the level of severity of students presenting to counseling and the relative lower percentage of students (versus those not in counseling) who actually die by suicide, it is thought that campus counseling is associated with a six-fold reduction in suicides among college students — something that can not only save lives and much heartache to parents/family, but also avoid enormous repercussions to the whole campus (e.g., campus being shut down in some instances, classes cancelled, residence hall floors being shut down, friends being distraught and unable to attend classes, copy-cat acts). There are some data from TAU, CAMS, and DBT research to suggest that these treatments are likely to be helpful to a significant number of the participants in this project. Study participation will include careful assessments of suicidal risk at least three times during the study—a level of monitoring far beyond that which CCC clients usually receive, helping raise student participants' awareness of their own suicidal risk. Regardless of treatment assignment, participants may derive a sense of accomplishment from participation in research and contributing to the knowledge of treatment for other students struggling with suicidal ideation. Given the demands and constraints of the pandemic, it is vital for the field to know whether a hybrid teletherapy/in-person format to provide care to suicidal college students can be done safely and effectively.

There are benefits to counselor participants as well, who will receive training in how to help students presenting with suicidal risk. Treating this population can be very distressing to counselors and receiving specialized training and ongoing case consultation was reported as a great benefit of participation by counselors in the pilot and feasibility study. Similarly, the CCCs may benefit from having guidelines on how to treat suicidal students participating in these studies via a hybrid teletherapy/in-person format. As noted in other sections of the proposal, counselors and CCCs are currently treating very distressed—and distressing—suicidal students

without much guidance. Participating in these studies gives them more knowledge and more guidance on how to proceed.

